## 8.8.3 Concomitant Medications

A secondary measure of safety will be the reporting of concomitant medications. All concomitant medications collected from Screening to Study Termination will be categorized as follows:

- Pretreatment medications are defined as medications taken prior to and after signing informed consent and those taken during the Preparatory Period prior to the first Experimental Session. A stop date is expected prior to the first Experimental Session for any medications requiring a change in dose, a skipped dose, or tapering.
- Treatment Period concomitant medications are defined as those taken or continued during the Treatment Period from the first Experimental Session to the last Integrative Session. A stop date is expected prior to the each Experimental Session for any medications requiring a change in dose, a skipped dose, or tapering.
- Concomitant medications with a start date of the day of and two days after IP administration
- Follow-up Period concomitant medications are defined as those taken or continued during the Follow-up Period after the last Integrative Session through Termination
- Any concomitant medications that are tapered
- Any concomitant medications that are taken to treat an AE
- Any concomitant medications that are taken to treat an SAE
- Any excluded concomitant medications taken as a deviation from the protocol.

Concomitant medications on case report forms will be classified using the WHO Drug Dictionary EnhancedTM (WHO DDE). Frequency and incidence of concomitant medications will be displayed by generic name, sorted by class, and summarized by treatment group, analysis set, and category as defined above. Concomitant medications will be analyzed and presented as follows:

- Concomitant medications taken on the day of and two days after IP administration will be presented separately
- Any psychiatric concomitant medications by period.

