3.3 Safety Objectives

The overall safety objective is to assess severity, incidence and frequency of AEs, AEs of Special Interest (AESIs), and Serious Adverse Events (SAEs), concomitant medication use, suicidal ideation and behavior, and vital signs to support the package insert for MDMA-assisted psychotherapy. The following safety objectives will evaluate the safety of MDMA-assisted psychotherapy.

- 1. Assess incidence of AEs during Experimental Sessions that may be indicative of a medical complication of the Investigational Product (IP), such as clinical signs and symptoms of chest pain, shortness of breath, or neurological symptoms or any other signs or symptoms that prompt additional vital sign measurements
- 2. Assess incidence of AEs by severity
- 3. Assess incidence of Treatment Emergent AEs (TEAEs) by severity
- 4. Assess incidence of TEAEs by severity taken during an Experimental Session and 2 days after IP administration
- 5. Assess incidence of AESIs, defined as AEs specified in the protocol related to cardiac function and abuse liability
- 6. Assess incidence of AEs by severity categorized as leading to discontinuation of IP, resulting in death or hospitalization, and continuing at Study Termination
- 7. Assess incidence of SAEs
- 8. Assess incidence of psychiatric concomitant medications taken during an Experimental Session and 2 days after IP administration
- 9. Assess incidence of any psychiatric concomitant medications taken during the Treatment Period

- MP16 Protocol Amendment 1 Version 1: 03 January 2018
- 10. Assess incidence of serious suicidal ideation and positive suicidal behavior assessed with the Columbia Suicide Severity Rating Scale (C-SSRS)
- 11. Assess mean changes in blood pressure, heart rate, and body temperature from pre-IP administration to end of each Experimental Session

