12.2 Allowed Concomitant Medications

The site physician may prescribe necessary and appropriate medications in accordance with local and state regulations during the study to treat AEs that do not respond to other management outlined in the Treatment Manual. Examples include concomitant benzodiazepines for uncontrolled anxiety (specifically, lorazepam at modest doses and occasional use only to avoid withdrawal effects of discontinuation between Experimental Sessions) or sleep aids (excluding trazodone) in compliance with Section 12.3 Prohibited Medications. Sublingual nitroglycerin will be available on site in the case of emergency.

Gabapentin or certain opiates will be allowed when prescribed for pain management. The following opiates will be allowed during the study: hydrocodone, morphine, and codeine. Prior to receiving study drug, participants who are taking opiates not included on this list will be cross-tapered to an allowable opiate under the care of their prescribing physician. Opiate medications may reduce the efficacy of MDMA and may prolong QT/QTc interval, but the opiates that are allowed during this trial have been selected because they have the lowest potential for QT/QTc interval prolongation. Individuals using opiates for pain management will be asked to decrease the dose leading up to the Experimental Session in order to avoid withdrawal effects when they are required to refrain from taking the medication from 12 hours before IP administration at the Experimental Session to 24 hours after. If a participant reports lack of analgesic effect during the sub-acute period following each Experimental Session, the site physician may cross-taper to a different allowed opiate medication.

If the participant is on stimulants for attention deficit/hyperactivity disorder (ADHD) at Baseline, they can continue to use them at the same dose and frequency, as long as they discontinue five half-lives before each Experimental Session and do not restart for 10 days after each Experimental Session.

All psychoactive medications, herbal supplements, nonprescription medications, and prescription medications must be reviewed by the research team. Failure to comply with protocol requirements for concomitant medications may result in withdrawal from treatment, depending on the investigator and Medical Monitor judgment.

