12.3 Prohibited Medications

To be enrolled in the study, participants must:

- Refrain from the use of any psychoactive medication not approved by the research team from Baseline through Study Termination (with the exception of gabapentin or certain opiates for pain control).
- Be willing to comply with all medication requirements per protocol. Medications will only be discontinued after enrollment per clinical judgment of the site physician in consultation with the prescribing physician.
- Agree that, for 1 week preceding each Experimental Session to refrain from:
 - o Taking any specified herbal supplement (except with prior approval of the research team).
 - Taking any nonprescription medications (with the exception of non-steroidal anti-inflammatory medications or acetaminophen) unless with prior approval of the research team.
 - Taking any prescription medications (with the exception of birth control pills, thyroid hormones, or other medications approved by the research team).

MP16 Protocol Amendment 1 Version 1: 03 January 2018

Use of Marijuana, St. John's Wort, and other herbs and medicines with notable serotonergic effects are prohibited from Baseline to Study Termination. Any investigational treatments under study for PTSD treatment are prohibited from use concurrent with this study.

Diphenhydramine is excluded from this study unless prior approval is granted by the site physician.

If an SSRI, SNRI, MAOI, or other antidepressant is used between Experimental Session 1 (Visit 5) and Study Termination (Visit 20), the participant will be withdrawn from treatment and continue in follow-up.

Opiates other than hydrocodone, morphine, and codeine are prohibited from Enrollment Confirmation to Study Termination. Participants taking prohibited opiates will be cross-tapered to an allowable opiate during the Preparatory Period.

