14.1.2 Safety Analyses

Safety data will be summarized by exposure to IP, unsolicited AEs, concomitant medications, suicidal ideation and behavior, and vital signs overall. If a participant has more than one AE mapped to the same PT, that AE will be reported once using the highest severity. AEs that occur on Day 0 (Experimental Session), Day 1, Day 2 after IP administration will be presented separately. Report incidence of AEs during Experimental Sessions such as clinical signs and symptoms, such as chest pain, shortness of breath, or neurological symptoms or any other signs or symptoms that may be indicative of a medical complication of the IP.

Frequency and incidence of concomitant medications will be displayed by generic name, sorted by class, and summarized by analysis set and category. Concomitant medications taken on Day 0 (Experimental Session), Day 1, Day 2 after IP administration will be presented separately. Any psychiatric concomitant medications will be tabulated by period (Preparatory, Treatment Period, Follow-up Period). Frequency and incidence of positive or serious ideation and suicidal behavior will be presented using descriptive statistics of C-SSRS scores in tabular format. Vital signs (heart rate, blood pressure, and body temperature) for Experimental Sessions will be summarized using descriptive statistics in tabular format listing values at pre-IP administration, prior to the supplemental dose, and at the end of each Experimental Session. Additional details are available in the Statistical Analysis Plan.

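### SAP 8.8.3 gives two conflicting rules for medications on Day 0 to 2 (start date versus taken), and no output for that window is limited to psychiatric medications as safety objective 8 is

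*SAP*

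**What the plan says.** Protocol 3.3, objective 8, repeated in SAP 3.3, reads: "Assess incidence of psychiatric concomitant medications taken during an Experimental Session and 2 days after IP administration". It is limited to psychiatric medications and is framed by use.

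Protocol 14.1.2 also works by use, but for all medications: "Concomitant medications taken on Day 0 (Experimental Session), Day 1, Day 2 after IP administration will be presented separately". It tabulates psychiatric medications by study period only.

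SAP 8.8.3 contains both rules:

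- In its list of categories: "Concomitant medications with a start date of the day of and two days after IP administration".
- In its list of presentations: "Concomitant medications taken on the day of and two days after IP administration will be presented separately".

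Between the two lists, the section says that frequency and incidence are summarised by the categories just listed. Its only output specific to psychiatric drugs is "Any psychiatric concomitant medications by period".

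The section also has a record-keeping convention for the Treatment Period: "A stop date is expected prior to the each Experimental Session for any medications requiring a change in dose, a skipped dose, or tapering".

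Three protocol passages bear on which records may be open at a session. Section 10.2.2.2 allows lorazepam or a sleep aid for severe persisting distress after a session. Section 12.2 describes benzodiazepine use as "specifically, lorazepam at modest doses and occasional use only to avoid withdrawal effects of discontinuation between Experimental Sessions". Section 12.3 lists what participants refrain from in the week before each session, including: "Taking any prescription medications (with the exception of birth control pills, thyroid hormones, or other medications approved by the research team".

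**The concern.** A medication that starts in a window and a medication that is used in a window are different things. The objective asks about use. The only Day 0 to 2 category in the SAP asks about start.

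The start-date wording cannot simply be dismissed as loose. The neighbouring Treatment Period and Follow-up Period categories are defined by use or continued use, so a programmer could fairly take the change of wording as deliberate. Because the incidence summary refers back to these categories, that programmer would build the table on start dates. Another could follow the later line and build it on use. Both would have followed the SAP.

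At stake is a named safety objective that belongs to a set meant to support the package insert. As-needed drugs are where the two rules can part, because one record may span more than one session.

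**Working it through.** No figure in the plan depends on this point, so there is none to reproduce. The check compares the two rules on each type of record that the documents make possible.

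**Step 1. Direction of the difference.** Let S be the records with a start date on Day 0, 1 or 2 of a session, and T the records with at least one dose on those days. If the start date is the date of first use and is complete, every record in S is also in T. So the count of S is at most the count of T. The difference is the records opened before the window and used within it.

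There is one limited exception. Under SAP 8.2.1, a missing start day in the month of first dosing is set to the first-dose day. That places the record on Day 0 of Session 1 by convention, whether or not the drug was used then.

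**Step 2. Record types.**

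| Record | Start-date rule | Taken rule |
|---|---|---|
| Rescue drug first used on Day 0 to 2 | counted | counted |
| Rescue drug stopped between sessions, new record opened on Day 0 to 2 of a later session | counted | counted |
| Rescue or sleep-aid record opened outside any window, still open, dose on Day 0 to 2 | missed | counted |
| As above, but opened on Day 0 to 2 of an earlier session | missed for the later session only | counted |
| Record open, no dose on Day 0 to 2 | not counted | not counted |
| Background opiate paused, resumed on Day 1 or 2 as a new record | counted | counted |
| Background opiate paused, resumed on Day 1 or 2, record left open | missed | counted |
| ADHD stimulant resumed after the 10-day pause in Protocol 12.2 | not counted | not counted |

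The rules part only where a record stays open across a session. The opiate row affects the all-medication table, not the psychiatric objective.

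**Step 3. Two illustrations (assumed records, not data).**

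- Lorazepam opened on Day 1 of Session 1, left open, and used after all three sessions: start date counts 1 of 3 windows, taken counts 3 of 3. Counted once per participant, both rules include this person.
- A sleep aid opened on Day 5 after Session 1 and used on the nights of Sessions 2 and 3: start date counts 0 of 2 windows, taken counts 2 of 2. Counted per participant, the start-date rule omits this person altogether.

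The loss therefore depends on the unit of incidence, and neither document states that unit for medications.

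**Step 4. Match to the objective.** Both Day 0 to 2 lines in SAP 8.8.3, and the one in Protocol 14.1.2, cover all medications. The psychiatric output in both documents is by period. No specified table crosses psychiatric medications with Day 0 to 2, so even the taken rule does not by itself deliver objective 8.

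**The case against.** The strongest reply is that the SAP does order a presentation by use, in agreement with the objective and with Protocol 14.1.2. Three statements out of four point the same way, and a sensible programmer would follow them. That stands to this extent: the defect is an unresolved inconsistency, and it cannot be said that use on Day 0 to 2 will be missed. It would be missed if the start-date category is the one used.

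The second reply is that open records should be uncommon. Lorazepam is for occasional use, prescription drugs are paused for a week before each session unless approved, and a skipped dose is expected to close the record. A rescue drug that is closed and reopened gets a new start date, and both rules count it. This also stands: the omission is the exception. It is not excluded, because the pause exempts drugs approved by the research team, and the stop-date convention does not clearly cover an as-needed record.

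A reader might also infer that the start-date rule pads the table with background drugs resumed after a protocol hold. It does not. An opiate resumed on Day 1 is also taken on Day 1, so both rules count it. What brings non-psychiatric drugs into the Day 0 to 2 lines is that those lines are not restricted to psychiatric medications.

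**Conclusion.** The point holds as an internal conflict in SAP 8.8.3, together with a missing output. One of the two Day 0 to 2 rules disagrees with safety objective 8 and Protocol 14.1.2. Given complete dates and a start date equal to first use, that rule can only equal or understate the quantity the objective asks for. An effect on the reported rate needs two conditions: the start-date category drives the table, and a record stays open across a session with a dose in the window. The absence of a psychiatric-only Day 0 to 2 output does not depend on either condition.

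The size cannot be computed. A reader might want to say that reported incidence is some fraction of true incidence, but the documents give neither a rate of rescue use nor a share of records left open. Any percentage would only restate an assumption.

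A reader might also infer that tolerability at the higher initial dose would look better than it was, since the loss falls mainly on Sessions 2 and 3. The documents do not support going that far: they specify no comparison of medication use by dose or by session.

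The consequence is confined to a descriptive safety table in a single-arm study. No primary or secondary result changes.

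**What to change.** In SAP 8.8.3:

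1. Replace the start-date condition in the Day 0 to 2 category with at least one dose taken on Day 0, Day 1 or Day 2, so that category, presentation and objective agree.
2. Add a Day 0 to 2 row limited to psychiatric medications, to answer objective 8.
3. State whether incidence is per session, per participant, or both.
4. Confirm that the Concomitant Medications eCRF captures dates of use for as-needed records. The form is not in the documents, so this may already be so; if not, add a date-of-use field for those drugs.

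No new visit or question is needed. Protocol 8.3.1 to 8.3.3 already have staff record or ask about medication at the end of the session, at the Integrative Session the next morning, and at the Day 2 call. The cost is an edit to one SAP section and, if use dates are not yet captured, a little more data entry. The sponsor should also accept that the reported rate may be less favourable.

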## 8.8.4 Analysis of Suicidal Ideation and Behavior

Suicidal ideation and behavior will be summarized according to suggestions made in the C-SSRS Scoring and Data Analysis Guide [1]. A positive response for suicidal ideation is counted when a participant answers "yes" to any one of the five suicidal ideation questions (Categories 1-5) on the C-SSRS (i.e., a score >0 for suicidal ideation). Serious suicidal ideation is a suicidal ideation score of 4 or 5. A positive response for suicidal behavior occurs when a participant answers "yes" to any one of the five suicidal behavior questions (Categories 6-10) on the C-SSRS (i.e., a score >0 for suicidal behavior). The number and percent of positive responses of Positive Ideation, Serious Ideation, and Positive Behavior will be tabulated by treatment group and time period (lifetime, screening, baseline, each Experimental Session (pre- and post-IP), Integrative Sessions, and endpoints). Frequency and incidence of positive or serious ideation and suicidal behavior will be presented using descriptive statistics in tabular format.

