Screening Multip weeks After		Multiple visits over 3 weeks/ After phone screen/ (-2 weeks/+1 week)	At initial visit, obtain Informed Consent and assess all screening measures (including PCL-5, Lifetime C-SSRS), medical history, and pre-study medications. Contact outside providers and order medical records, physical exam, labs (including pregnancy and drug tests), ECG, and 1-minute rhythm strip. Once all results and records are obtained, review along with notes from all screening visits and measures. If eligible, send results of LEC-5 & SCID-5-SPQ to IR. Screening may take place over 3 weeks at multiple visits.	
	Independent Rater Screening	1 hour/ 2 days after initial eligibility established during Screening/ (+7 days)	After PCL-5 and initial eligibility are reviewed, an IR will conduct the Since Last Visit C-SSRS, SCID-5-PD, DDIS, and MINI via telemedicine. Results will be confirmed by clinical observation during the Preparatory Period, but the SCID-5-PD, DDIS, and MINI will not be repeated.	
Enrollment	Enrollment (Visit 0)	1.5 hours/ 2 days after Independent Rater Screening (+12 days)	Prior to enrolling: review all screening measures, medical history, discussion with outside providers and sponsor, and any clarification phone calls with participant. Visit is 1.5 hours to review eligibility and medical tapering plan. If enrolled, begin taper, (5 half-lives plus 1 week for stabilization). Adverse Event (AE) collection begins.	

	Preparatory Period with Enrollment Confirmation			
From Preparatory Session 1 (Visit 1) to Preparatory				
Study Visit #		Visit Duration/ Visit Timing/	Brief Description of Events	
V ISIL T	•	(Scheduling Window)		
riod	Preparatory Session 1 (Visit 1)	1.5 hours/ Within 1 week (0 to 12 days) of Enrollment (V0)	90-minute Preparatory Session. Target visit timing on tapering needs. If needed, schedule calls between V1 and V2 if indicated for tapering, safety, or further questions about medical history.	
Preparatory Period	Preparatory Session 2 (Visit 2)	1.5 hours/ Within 3 weeks of V1	90-minute Preparatory Session/ongoing assessment. If tapering is complete or not needed, check eligibility and schedule V3 and V4. If tapering is ongoing, schedule post taper call for ongoing assessment.	
	Phone Call End Taper	1 hour/ Within 1 week of taper end & 8 weeks of V0	If needed, confirm medication taper and stabilization is complete and participant is eligible for Baseline CAPS-5. Schedule V3 and V4.	

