5.2 Planned Duration of Study

IND #063384

Full screening may take 2 to 6 weeks after completion of phone screening. The Preparatory Period begins at enrollment and can be as brief as 2 weeks, but depending on medication tapering could be as long as 11 weeks to ensure an appropriate medication washout of at least five halflives of pre-study psychiatric medications and active metabolites, and at least one additional week for stabilization.

Enrollment Confirmation takes place at the completion of the Preparatory Period, at which time the Treatment period will commence. The approximately 12-week Treatment Period will consist of three Experimental Sessions 3 to 5 weeks apart with associated non-drug Integrative Sessions and CAPS-5 assessments.

After the final Integrative Session 3.3 (Visit 18), participants will enter follow-up with no study visits for approximately 4 weeks, after which the Primary Outcome CAPS-5 T4 assessment will take place. Although there are allowable windows for all visits throughout the protocol, the

overall timelines should comply with the target timing of the Primary Outcome CAPS-5 T4 assessment, which must be completed 18 weeks (+/- 3 weeks) post Baseline, even if the maximum possible visit windows were used between visits. Other visits should be scheduled to ensure the timing of the Primary Outcome CAPS-5 T4 assessment is appropriate. The Study Termination visit follows 1 to 9 days after the final CAPS-5 assessment.

The minimum time that a participant who completes all study visits from Screening to Study Termination will be in the clinical trial is 19 weeks, and the maximum is 38 weeks. The average participant is expected to complete the study in 27 weeks. Any delays between visits outside of the protocol-defined windows may result in a corresponding extension of study duration and should be documented as a deviation as appropriate.

All participants who complete the study will be asked to participate in a LTFU extension study with one visit 12 months after the last Experimental Session.

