7.3 Safety Measures

C-SSRS (Columbia Suicide Severity Rating Scale)

The C-SSRS is a clinician-administered measure of suicidal behavior devised to detect potential suicidal thoughts or behaviors during a clinical trial [65]. It consists of a Lifetime version and a Since Last Visit version that assess suicidal ideation, ideation intensity, and behavior. The C-SSRS consists of a series of questions, and can be administered during a face-to-face interview or over the telephone. The Lifetime version will only be administered at the initial Screening visit. All subsequent administrations will utilize the Since Last Visit version. Participants who are discontinuing medications to participate in the study will complete the C-SSRS before and after medication washout. The C-SSRS Intensity scale for Lifetime obtained a Cronbach's alpha of 0.93 and 0.94 for the Since Last Visit form, and Last Visit C-SSRS severity scores were positively correlated with the BDI "suicide thoughts" item [66].

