8.2.3 Baseline: Preparatory Session 3 & Enrollment Confirmation

Prior to Visit 4, the site team will review the results of the IR visit to ensure that the CAPS-5 Total Severity Score is at least 35. Visit 4 should be scheduled within 6 days of the Baseline CAPS-5 assessment but ideally will take place as close to Experimental Session 1 (Visit 5) as possible, but not on the same day.

At Visit 4, the site team will confirm eligibility by reassessing specified eligibility criteria and ensuring that the participant continues to agree to all lifestyle modifications. If the participant

continues to be eligible for the study, enrollment will be confirmed (after approval from the Medical Monitor for the initial participants until confidence is established). If any requirements are not met before or during Visit 4, the participant will be considered a Pre-Dosing Early Termination.

For eligible participants at Visit 4, qualified site staff will ensure at least 3 hours are scheduled for the visit and:

- Perform urine pregnancy test for participants who are of childbearing potential.
- Perform urine drug test.
- Administer Since Last Visit C-SSRS to determine suicidal risk.
- Actively support participant in the completion of Baseline self-reported measures:
 - o PCL-5- ensure assessment is in relation to index trauma
 - o ACE
 - o BDI-II
 - CPGS
 - o EQ-5D-5L
 - o IASC
 - o IPF
 - o SCS
 - o TAS-20
 - o SRNU
 - o EAT-26
 - o HPQSF
 - UFEC

Completion of the measures does not need to be recorded.

- Complete the third 90-minute Preparatory Session (as described in Section 8.2.1 Preparatory Sessions 1 and 2) with the purpose of confirming all enrollment is met and completing final preparation for the first Experimental Session.
- Remind the participants of lifestyle modifications, including fasting and refraining from using psychoactive or non-approved medications, pertinent prior to the Experimental Session per Section 4.3 Lifestyle Modifications.
- Schedule Visit 5.

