#### 8.0 Analyses

Every effort will be made to ensure complete, accurate and timely data collection and to avoid missing data, to ensure the completeness of the data which can impact the integrity and accuracy of the final study analysis. The statistical analyses will be reported using summary tables, figures, and data listings. All analyses and tabulations will be performed using SAS® Version 9.4 or higher, and S-PLUS. In general, nominal variables will be described in terms of frequencies and percentages. Ordinal and non-normal continuous variables will be described using sample median and range.

Approximately normal variables will be described using sample mean and standard deviations and analyzed by parametric statistical tests. Except for the primary effectiveness analysis, all statistical tests will be two-sided and a difference resulting in a p-value of less than or equal to 0.05 will be considered statistically significant. All p-values will be rounded to and displayed in four decimals. If a p-value less than 0.0001 occurs it will be shown in tables as <0.0001. Data not subject to analysis according to this plan will not appear in any tables or graphs, but will be included in the data listings. Selected results may be presented graphically using standard graphical software.

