#### 8.4 Baseline Values

Baseline values are from Baseline Visits for all measures, except C-SSRS, AUDIT, DUDIT, resting blood pressure (BP), Body Mass Index (BMI). For C-SSRS, the initial screening visit will be conducted with the 'Lifetime' version of the measure. The Independent Rater Screening assessment of 'Since Last Visit' suicidal ideation and behavior will be used as 'Baseline.' For the AUDIT and DUDIT measures and resting BP, BMI, results collected at Screening will be used as the Baseline value.

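### SAP 8.8.4 reports C-SSRS positives period by period with no within-participant comparison, so new or worsened ideation at scores 1-3 can go unseen; a shift table from V5 pre-IP would show it

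*SAP*

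**What the plan says.** SAP 8.8.4 defines positive ideation as any score above 0, serious ideation as 4 or 5, and positive behavior as any behavior item answered yes. The planned table is this: "The number and percent of positive responses of Positive Ideation, Serious Ideation, and Positive Behavior will be tabulated by treatment group and time period". The periods listed are lifetime, screening, baseline, each Experimental Session before and after IP, Integrative Sessions, and endpoints. The section closes by promising frequency and incidence in descriptive form, without defining incidence, and it refers to a published C-SSRS scoring guide. Protocol 14.1.2 says that the results "will be presented using descriptive statistics of C-SSRS scores in tabular format".

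SAP 8.4 fixes the reference value: the Independent Rater Screening form of "suicidal ideation and behavior will be used as" Baseline. SAP 8.8.5, by contrast, plans change from baseline for vital signs.

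On timing, taper starts after that form, at Visit 0 (Protocol Table 1): "If enrolled, begin taper, (5 half-lives plus 1 week for stabilization". Protocol 7.3 adds: "Participants who are discontinuing medications to participate in the study will complete the C-SSRS before and after medication washout". Protocol 8.3.2 and footnote C of SAP Table 3 schedule further C-SSRS forms at the Day 2 and Day 7 calls after each session.

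**The concern.** Protocol 10.1.2 recognises that trauma-focused work can worsen suicidal ideation during and shortly after sessions. Worsening is a within-person question, and with no control arm the participant's own pre-dose form is the only internal reference. Separate percentages per period fix only the margins of the before-after table. Participants who become positive can be balanced by others who resolve, and movement within scores 1-3 stays inside one row.

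At stake is how clearly the study describes a safety outcome that falls under its overall safety objective and that the SAP itself chose to report as Positive Ideation. The primary result is not affected.

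**Working it through.** **1. Where the call forms sit.** C-SSRS (10 minutes) is the only measure ticked in the V5, V10 and V15 columns of SAP Table 3, and the stated total is 40 minutes. Pre- and post-IP forms alone give 2 × 10 = 20, which does not match. Pre-IP, post-IP, Day 2 and Day 7 give 4 × 10 = 40, which does. Table 3 thus places the call forms with the Experimental Session. SAP Table 2 ticks the calls themselves under V6, V11 and V16, and 8.8.4 names no call period.

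**2. How many forms.** After the first dose a completer has V5 post-IP (1), pre- and post-IP at V10 and V15 (4), Day 2 and Day 7 calls (6), Integrative Sessions (9) and V20 (1), which makes 21. The calls are 6/21 = 28.6%.

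**3. What the margins leave open.** Take n = 60 (the protocol maximum), b positive before and a positive after. The number of new cases lies between max(0, a − b) and min(a, 60 − b). The rates below are assumptions.

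| Before | After | New cases possible |
|---|---|---|
| 6 (10%) | 6 (10%) | 0 to 6 |
| 12 (20%) | 12 (20%) | 0 to 12 |
| 18 (30%) | 18 (30%) | 0 to 18 |
| 12 (20%) | 9 (15%) | 0 to 9 |

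The upper ends need complete turnover. As a milder case, 6 new and 6 resolved with b = 12 shows as 12/60 twice, although 6/48 = 12.5% of those negative before became positive. If nobody has serious ideation before dosing, every later serious case is new and nothing is masked.

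**4. Which pre-dose form to use.** Visit 0 falls 2 to 14 days after Independent Rater Screening. Protocol 5.2 starts the Preparatory Period at enrollment and says it "can be as brief as 2 weeks, but depending on medication tapering could be as long as 11 weeks". So the Baseline form precedes the end of that period by 2 + 14 = 16 to 14 + 77 = 91 days. Protocol 8.2 lets the period start up to 12 days after Visit 0, which raises the maximum to 14 + 12 + 77 = 103 days. For participants who taper, pairing with this form would mix withdrawal with MDMA. The V5 pre-IP form follows washout and precedes dosing.

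**5. Recall windows**, taking the last visit to be the previous C-SSRS form. V4 is within 6 days of V3, V5 within 1 week of V3, and V4 "ideally will take place as close to Experimental Session 1 (Visit 5) as possible, but not on the same day", so V5 pre-IP covers 1 to 7 days. Post-IP covers about 8 hours, Day 2 about 1 day, Day 7 about 5 days, and V20 about 4 weeks (±2). Only Day 7 is close to V5 pre-IP. As an extreme, with 10% positive per 5 days and independent days, the rate would be 1 − 0.9^(1/15) = 0.7% over 8 hours, 1 − 0.9^(1/5) = 2.1% over 1 day and 1 − 0.9^(28/5) = 45% over 28 days.

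**6. Chance movement with no drug effect.** Assume 10% positive per form and between-form correlation ρ. One form against one form gives 60 × 0.1 × 0.9 × (1 − ρ) new cases and the same number resolved: 3.8 at ρ = 0.3, 2.7 at 0.5, 1.6 at 0.7. For pooled forms at ρ = 0.5, let N(k) be the beta-binomial probability of being negative on k forms: N(1) = 0.900, N(3) = 0.8265, N(4) = 0.8058, N(21) = 0.6887, N(24) = 0.6797.

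- One form against any of three: new 60 × (0.900 − 0.8058) = 5.6; resolved 60 × (0.8265 − 0.8058) = 1.2.
- Three pre-dose against 21 post-dose: new 60 × (0.8265 − 0.6797) = 8.8; resolved 60 × (0.6887 − 0.6797) = 0.5.

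Pooling therefore produces apparent worsening from nothing.

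**The case against.** The strongest reply is that the plan may already cover this. The scoring guide that 8.8.4 adopts might call for shift tables, and the undefined incidence might mean a count of participants with an event. Neither can be settled from the documents, so the point is confined to what the SAP writes out.

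The other backstops are real but partial. The adverse-event definition in Protocol 11.1 includes exacerbation of existing conditions, the therapy team that records events also gives most C-SSRS forms, and SAP 9.0 provides ongoing listing reviews, which are readable with at most 60 participants. However, the explicit instruction in Protocol 10.1.2 to record increases in suicidality as adverse events sits in the pathway triggered by ideation of 4 or more or by positive behavior. For scores 1-3 capture depends on recognition at the site. Score summaries under Protocol 14.1.2 could move with a rise from 1 to 3, but they are unpaired too.

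Three stronger readings do not stand:

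- A reader might infer from SAP 8.0, "Data not subject to analysis according to this plan will not appear in any tables or graphs", that the Day 2 and Day 7 forms will drop out of the tables. C-SSRS data do have a planned analysis, and Table 3 puts these forms with the Experimental Session. What remains is a labelling ambiguity, not a shown omission.
- A reader might infer that the plan lacks any post-washout reference. It does not: V5 pre-IP is already its own column at the level of percentages. Only the pairing is missing.
- A reader might infer that new serious ideation or behavior would be hidden. It is largely visible, and it is what the numbered C-SSRS objective names.

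**Conclusion.** The point holds as a minor, cheap improvement. The written analysis cannot show how many participants developed new ideation at scores 1-3 after dosing, and it is blind to a rise from 1 to 3 in its three rows. The size is unknown: no ideation prevalence is given and, with equal or falling percentages, the lower bound on hidden cases is zero. The ranges above rest on assumed rates and n = 60. The pre-taper Baseline form is a poor paired reference for participants who taper; V5 pre-IP is better and is already collected. Confidence is medium because the scoring guide cannot be seen.

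**What to change.** In SAP 8.8.4:

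1. Name the Day 2 and Day 7 calls as time points in their own right.
2. Add a descriptive shift table on the Safety Set with categories none, ideation 1-3, ideation 4-5 and behavior. Use V5 pre-IP alone as the reference, against the post-IP, Day 2 and Day 7 forms of each session and V20, each shown separately. Add the number of participants with any increase in the highest ideation score.
3. State each form's recall window under the table, and do not pool forms worst-against-worst.

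The cost is some SAP wording and one or two tables from data already collected. The downside is interpretive. There is no control for natural fluctuation, so about 3 new cases of 60 is not a signal by itself. Recall windows also differ: post-IP and Day 2 lean toward apparent resolution and V20 toward apparent worsening, which makes Day 7 the most comparable column. Session 2 and 3 pre-IP forms follow earlier MDMA, so shifts from them would be supplementary only.
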